3 STATISTICAL METHODS

3.1 General Considerations

Data will be presented in data listings sorted by cohort and treatment, subject number and date collected, where appropriate. Tabular summaries will be presented by cohort and treatment group. Categorical data will be summarized by the number and percentage of subjects within each category. In general, continuous variables will be summarized by descriptive statistics including mean, standard deviation, median, minimum, and maximum.

The last observation carried forward (LOCF) will be used in efficacy and pharmacodynamics (PD) endpoints analyses unless otherwise specified. Baseline values will be defined as the last valid assessment prior to the first administration of study treatment unless otherwise specified.

All statistical tests will be 2-sided at an alpha = 0.1 significance level unless stated otherwise. There will be no adjustment for multiplicity.

Data analyses will be performed using SAS[®] version 9.3 or higher (SAS Institute Inc., Cary, NC).

3.2 Analysis Populations

The analysis populations are defined in Table 3.2-1.

Table 3.2-1 Analysis Populations

Population	Description
Intent-to-treat (ITT) population	Subjects who receive any study investigational product will be included in the ITT population and subjects will be analyzed according to their randomized treatment group.
As-treated population	Subjects who receive any study investigational product will be included in the as-treated population will be analyzed according to the treatment they received.
PK population	The PK population includes all subjects who received at least one dose of MEDI0382 and had at least one post-baseline MEDI0382 PK sample with a value above the lower limit of quantitation.
PD population	The PD population includes all subjects who received at least one dose of investigational product and had at least one post-baseline PD sample or PD evaluation [REDACTED]

3.3 Study Subjects

3.3.1 Subject Disposition and Completion Status

A summary of subject eligibility and randomization as well as treatment group received (including summary of subjects randomized but not treated) will be provided. In addition, disposition of subjects throughout the study with respect to completion of treatment and follow-up will be provided.

3.3.2 Demographics and Baseline Characteristics

Demographic information and baseline characteristics will be summarized by cohort and by treatment group. Demographic information will include: gender, age (years), ethnicity, race, weight (kg), height (cm), and body mass index (BMI) (kg/m²). A summary of baseline characteristics may include but not limited to eGFR, HbA1c, glucose, insulin, blood pressure, and pulse rate etc.

$$\text{BMI} = \text{weight (kg)} / [\text{height (m)}]^2$$

All summaries of continuous characteristics will be based on non-missing observations. For categorical characteristics, percentage will be calculated, and the denominator for each percentage is the number of subjects with non-missing data for that demographic or baseline parameter.

No statistical test will be performed for comparison of any baseline measurement among treatment groups.

3.3.3 Study Drug Exposure

The number of doses and total dose received will be summarized for each investigational product (MEDI0382 or Placebo) by descriptive statistics and by frequency.

3.3.4 Concomitant Medications

Concomitant medications will be coded using current WHO Drug Dictionary. The number and percentage of subjects who took concomitant medications will be summarized by the highest anatomical therapeutic chemical (ATC) class and preferred term by treatment group for each cohort for the As-treated Population. The summary of concomitant medications will include all concomitant medications taken on or after the date of first dose of investigational product or any concomitant medication started prior to first dose of investigational product that continued beyond the date of first dose of investigational product.

3.4 Efficacy Analyses

3.4.1 Primary Efficacy Endpoint(s) and Analyses

3.4.1.1 Primary Efficacy Endpoint(s)

The co-primary endpoints for this trial are:

1. Percentage change in plasma glucose AUC_{0-4hr} as measured by a standardized MMTT from baseline (Day -1) to the end of 49 days of treatment (Day 49)
2. Percentage change in body weight from baseline (Day 1) to the end of 49 days of treatment (Day 50)

3.4.1.2 Primary Efficacy Analysis

The percent change in the MMTT plasma glucose $AUC_{0-4mmtt}$ from the baseline (Day -1) evaluation to the Day 49 evaluation will be analyzed with an analysis of covariance (ANCOVA) with an effect for treatment (MED0382 or Placebo) and the baseline MMTT glucose AUC_{0-4hr} value used as a covariate (Cohort 1).

The percent change in body weight from baseline (Day 1) to the Day 50 evaluation will also be analyzed with an ANCOVA with an effect for treatment (MED0382 or Placebo) and the baseline body weight used as a covariate (Cohort 1).

Both comparisons will be performed at the 0.05 significance level (2-sided).

3.4.2 Secondary Efficacy Endpoint(s) and Analyses

3.4.2.1 Secondary Efficacy Endpoint(s)

1. Change in HbA1c from baseline (Day -1) to the end of 49 days of treatment (Day 49) (Cohort 1)
2. Change in fasting plasma glucose (Day -1) from baseline to the end of 49 days of treatment (Day 49) (Cohort 1)
3. Change in body weight (kg) from baseline (Day 1) to the end of 49 days of treatment (Day 50) (Cohort 1)
4. Proportion of subjects achieving > 5% body weight loss from baseline (Day 1) after 49 days of treatment (Day 50) (Cohort 1)
5. Percent change in MMTT plasma glucose AUC_{0-4hr} from baseline (Day -1) to Day 7 (Cohorts 1 and 2 combined)

3.4.2.2 Secondary Efficacy Analyses

All analyses will be performed at the 0.05 (2-tailed) significance level unless otherwise specified.

The changes from baseline in HbA1c, fasting plasma glucose, and body weight will be analyzed using an ANCOVA with an effect for treatment and the corresponding baseline measure as a covariate. The pre-meal plasma glucose values from the MMTT are used for the fasting plasma glucose values. The proportion of subjects who have a >5% decrease in body weight will be analyzed with logistic regression with treatment effect and the baseline weight as a covariate.

The percent change in MMTT glucose AUC from baseline to Day 7, including data from both cohorts, will be analyzed with an ANCOVA with treatment effect and the baseline value used as a covariate.

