1.7.2 Secondary Hypotheses

- Administration of MEDI0382 once daily titrated up to a dose level of 300 µg across 49 days will have an acceptable safety profile and be well tolerated in overweight and obese subjects with T2DM
- Administration of MEDI0382 once daily titrated up to a dose level of 300 µg from 50 µg will have a predictable PK profile
- Administration of MEDI0382 once daily at a dose level of 50 µg will result in superior blood glucose control versus placebo after 7 days of treatment in overweight and obese subjects with T2DM

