3 STUDY DESIGN

3.1 Description of the Study

3.1.1 Overview

This is a randomised, double-blind, placebo-controlled study to evaluate the efficacy, safety, tolerability, and PK profile of 50 and 300 µg of MEDI0382 in overweight and obese subjects with T2DM. Up to 63 subjects are planned to be enrolled across multiple study sites.

The study is divided into 2 cohorts that will be recruited in parallel; for both cohorts, subjects will be consented, screened for suitability, and randomised within 60 days if eligible. A total of 39 subjects will be randomised to Cohort 1, and 24 subjects will be randomised to Cohort 2. Cohort 1 will evaluate the efficacy, safety, tolerability, and PK of MEDI0382 when titrated up in weekly intervals from 50 to 300 µg and administered over 49 days. Cohort 2 will explore an alternative 2-week titration schedule, and will provide additional information on the PK profile and glucose-lowering efficacy of 50 µg MEDI0382

Cohort 1

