^d Cohort 1 only; subjects should be shown the device and given an explanation as to how it is worn; allocation to Cohort 2 may be preferable for subjects who would rather not use a CGM device during the study.

^e Subject's ability to self-administer investigational product will be verified using normal saline subcutaneous injections.

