2.2 Study Design

This is a randomized, double-blind, placebo-controlled study to evaluate the efficacy, safety, tolerability, and PK profile of 50 and 300 µg of MEDI0382 in overweight and obese subjects with T2DM. Up to 63 subjects are planned to be enrolled across multiple study sites. The study is divided into 2 cohorts that will be recruited in parallel; for both cohorts, subjects will be consented, screened for suitability, and randomized within 60 days if eligible. A total of 39 subjects will be randomized to Cohort 1, and 24 subjects will be randomized to Cohort 2. Cohort 1 will evaluate the efficacy, safety, tolerability, and PK of MEDI0382 when titrated up in weekly intervals from 50 to 300 µg and administered over 49 days. Cohort 2 will explore an alternative 2-week titration schedule, and will provide additional information on the PK profile and glucose-lowering efficacy of 50 µg MEDI0382 [REDACTED]. Each dose is administered as an SC injection each morning according to the dosing schedule is presented below:

Figure 2.2-1 Study Flow Diagram

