2.3 Treatment Assignment and Blinding

An interactive web response system (IWRS) will be used for randomization to a treatment group and assignment of blinded investigational product kit numbers. A subject is considered randomized when the IWRS provides the assignment of blinded investigational product kit numbers for the subject.

In Cohort 1, subjects will be randomized using a ratio of 2:1 to one of 2 treatment arms to receive either MEDI0382, titrated from 50 µg up to 300 µg according to a fixed schedule, or placebo for 49 days.

In Cohort 2, subjects will be randomized using a ratio of 3:1 to receive either MEDI0382, titrated from 50 µg up to 300 µg according to a different fixed schedule, or placebo for 49 days.

This is a double-blind study in which MEDI0382 and placebo are identically labeled and indistinguishable in appearance so that neither the subject nor any of the investigator or sponsor staff who are involved in the treatment or clinical evaluation of the subjects or data analysis will be aware of the treatment received (ICH E9).

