3.4.3 Other Efficacy Analyses

For Cohort 2 data, the percent change in the MMTT plasma glucose AUC_{0-4hr} from the baseline (Day -1) evaluation to the Day 7, Day 14, and Day 49 evaluations will be summarized by visit and analyzed for the end-of-treatment measure at Day 49 only with a similar ANCOVA model as that in the primary analysis.

Similar summary and analysis will be also applied to the change in fasting plasma glucose from baseline (Day -1) to the Day 7, Day 14, and Day 49 evaluations (Cohort 2 only), the change and percent change in body weight from baseline (Day 1) to the Day 8, Day 15, and Day 50 evaluations (Cohort 2 only), and the change in HbA1c from baseline (Day -1) to the Day 49 evaluations.

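### The pooled Day-7 glucose AUC model omits cohort although treatment is randomised 2:1 and 3:1 within cohort; adding the term is a minor, nearly free improvement

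*SAP*

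**What the plan says.** SAP 3.4.2.2 tests the 50 µg dose by pooling the cohorts. The Day-7 endpoint (percent change in glucose AUC), "including data from both cohorts, will be analyzed with an ANCOVA with treatment effect and the baseline value used as a covariate". Protocol 4.8.3.2 asks for a model of the same form as the primary one (treatment and baseline). Neither document names cohort as a factor.

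Randomisation is separate by cohort. SAP 2.3 states "In Cohort 1, subjects will be randomized using a ratio of 2:1" and "In Cohort 2, subjects will be randomized using a ratio of 3:1". Protocol 4.1.1 gives the planned numbers: 26 active and 13 placebo in Cohort 1, 18 active and 6 placebo in Cohort 2.

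How a subject comes to be in one cohort or the other is not clear:

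- Protocol 3.1.1: "A total of 39 subjects will be randomised to Cohort 1, and 24 subjects will be randomised to Cohort 2". SAP 2.2 says the same.
- Protocol 4.2.1, footnote d to the screening schedule: "allocation to Cohort 2 may be preferable for subjects who would rather not use a CGM device during the study".
- Protocol 4.6.1 describes randomisation to treatment within each cohort, but no random step that decides the cohort.

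The test serves a stated secondary hypothesis (Protocol 1.7.2), that 50 µg "will result in superior blood glucose control versus placebo after 7 days of treatment in overweight and obese subjects with T2DM". It is the only planned between-arm test of Day-7 MMTT glucose AUC. For Cohort 2 alone, SAP 3.4.3 says the AUC changes "will be summarized by visit and analyzed for the end-of-treatment measure at Day 49 only".

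**The concern.** With different allocation ratios, treatment and cohort are correlated by design once the cohorts are pooled. Randomisation protects the comparison within each cohort. The pooled two-arm comparison is protected only if the cohorts respond alike, given baseline AUC.

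They might not. Footnote d allows CGM preference to steer subjects to Cohort 2. Procedures up to Day 7 also differ: Cohort 1 has CGM and ambulatory blood pressure monitoring, while Cohort 2 has neither but has obligatory overnight stays and full PK profiles on Days 1 and 7.

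A cohort difference would do two things to the planned analysis. Part of it would shift the estimated 50 µg effect, and the spread between cohorts within each arm would enlarge the residual variance and reduce power. The by-cohort summaries in SAP 3.1 would reveal such a difference but would not remove it from the pooled estimate.

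**Working it through.** **Inputs.** Counts 26/13 and 18/6 (Protocol 4.1.1). Target difference 12 points with 80% power for 44 against 19 (Protocol synopsis, SAP 2.4). Two-sided 0.05 (SAP 3.4.2.2). The visible text gives no SD for Day 7; Protocol 4.8.2 is redacted in the public copy. No cohort difference D is given either, so 2, 5 and 10 points are assumed.

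**The plan's own figures.** For Cohort 1 (26 against 13, noncentral t, two-sided 0.05), a difference of 28 with SD 20 gives 98.0% (stated 97%), and 2.3 with SD 2.2 gives 85.0% (stated 85%). The planning method is therefore clear. The Day-7 figure cannot be reproduced without an SD. Solved backwards, 80% power for 12 points with 44 against 19 requires SD 15.36 at two-sided 0.05 (17.4 at 0.10).

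**Share of a cohort difference that enters the effect.**
18/44 − 6/19 = 0.4091 − 0.3158 = 0.0933.
Bias = 0.0933 × D = 0.19, 0.47 and 0.93 points for D = 2, 5 and 10.

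**Added residual variance.** Pooled within-arm variance of the cohort indicator = (18×26/44 + 6×13/19)/61 = (10.64 + 4.11)/61 = 0.2417. The residual variance rises by 0.2417 × D²: 6.0 at D = 5 and 24.2 at D = 10, which is 2.6% and 10.2% of 15.36² = 235.9.

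**Cost of the term.** Squared correlation of treatment and cohort = (26×6 − 13×18)²/(39×24×44×19) = 6084/782,496 = 0.0078. About 99% of the treatment contrast is therefore already within cohort. The variance factor goes from 1/44 + 1/19 = 0.07536 to 0.07595, a ratio of 1/(1 − 0.0078) = 1.0078. Residual degrees of freedom go from 60 to 59. Calculated power goes from 80.0% to 79.6% at SD 15.36.

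**Power by simulation.** 100,000 runs per row, normal errors, true effect −12, two-sided 0.05. A baseline covariate unrelated to the outcome is fitted, which is why the first row starts slightly below 80%.

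| SD 15.36 taken as | Cohort 2 response | Without cohort | With cohort |
|---|---|---|---|
| within cohort | no difference | 79.2% | 78.9% |
| within cohort | 2 worse | 78.2% | 79.1% |
| within cohort | 5 worse | 75.4% | 79.1% |
| within cohort | 10 worse | 69.4% | 79.1% |
| within cohort | 5 better | 81.8% | 79.3% |
| within cohort | 10 better | 82.6% | 79.0% |
| total | 5 worse | 76.6% | 80.2% |
| total | 10 worse | 73.7% | 83.2% |
| total | 10 better | 86.2% | 83.1% |

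The "total" rows assume that 15.36 already includes cohort spread, so the within-cohort SD is 15.16 at 5 points and 14.55 at 10. Where Cohort 2 responds better, part of the power without the term comes from bias away from zero.

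**Type I error**, without and with the term: 4.9% and 5.1% at D = 5; 4.4% and 4.9% at D = 10.

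**Other counts.** The 9.3% share holds only at planned numbers:

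- One Cohort 2 placebo subject without a Day-7 value: 18/44 − 5/18 = 13.1%.
- Three Cohort 2 active subjects without one: 15/41 − 6/19 = 5.0%.
- Five replacements per cohort (the maximum in Protocol 4.1.7), if they gave 29:15 and 22:7: 22/51 − 7/22 = 11.3%.

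**The case against.** Nothing in the documents points to a Day-7 cohort difference. Both cohorts recruit in parallel under one set of eligibility criteria, receive the same 50 µg dose through Day 7, and take the same meal after the same fast and dosing interval. Protocol 4.8.3.2 already restricts the AUC to the sampling times common to both cohorts, and baseline AUC is in the model. No document links reluctance to wear a CGM device with glucose response. A residual difference of 10 points would be nearly as large as the 12-point treatment target.

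The direction is also unknown. Averaged over both directions at 5 points, power without the term is (75.4 + 81.8)/2 = 78.6%, against (79.1 + 79.3)/2 = 79.2% with it. On mean squared error, the term adds (0.07595 − 0.07536) × 235.9 = 0.14 of variance, while omitting it adds squared bias of 0.0933² × D² = 0.0087 D². These are equal at D of about 4 points, and below that the planned model is slightly more accurate.

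All of this stands, and it is why the point is minor. It does not remove the case for the term. The averaged power credits the planned model with gains that come partly from bias, and the most the term can cost is very small. The share that leaks also depends on which of only six planned Cohort 2 placebo subjects have Day-7 values, which cannot be known in advance.

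**Conclusion.** The point holds as a modest improvement, not as the correction of an error. The pooled Day-7 model ignores the groups within which the trial randomises. At planned counts, 9.3% of any cohort difference beyond baseline AUC enters the 50 µg effect: 0.2 to 0.9 points for assumed differences of 2 to 10 points.

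With a within-cohort SD of 15.36, an unfavourable difference of that size takes power to between 78% and 69%, against 79% with the term. These figures rest on an assumed cohort difference and on an SD back-calculated from the stated 80%. The direction of any bias is unknown, type I error is not inflated, and the co-primary analyses use Cohort 1 only. The change is worth making because it aligns the only planned between-arm test of Day-7 MMTT glucose AUC with the randomisation at almost no cost.

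**What to change.** In SAP 3.4.2.2, specify the Day-7 analysis as an ANCOVA of percent change in glucose AUC with treatment, cohort (1 or 2) and baseline AUC, and do so before unblinding so that the model is not chosen after the data are seen. No other model, sample size or data collection needs to change for this point.

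The cost is 1 degree of freedom (60 to 59), 0.8% more variance of the treatment estimate, and about 0.3 to 0.4 points of power if the cohorts do not differ.

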3.4.3 Other Efficacy Analyses

For Cohort 2 data, the percent change in the MMTT plasma glucose AUC_{0-4hr} from the baseline (Day -1) evaluation to the Day 7, Day 14, and Day 49 evaluations will be summarized by visit and analyzed for the end-of-treatment measure at Day 49 only with a similar ANCOVA model as that in the primary analysis.

Similar summary and analysis will be also applied to the change in fasting plasma glucose from baseline (Day -1) to the Day 7, Day 14, and Day 49 evaluations (Cohort 2 only), the change and percent change in body weight from baseline (Day 1) to the Day 8, Day 15, and Day 50 evaluations (Cohort 2 only), and the change in HbA1c from baseline (Day -1) to the Day 49 evaluations.

3.5 Exploratory Pharmacodynamic Endpoint(s) and Analyses

3.5.1.1 Pharmacodynamic Endpoint(s)

- [REDACTED]
- Change in CGM glucose AUC_{0-24h} from baseline (Day -1) to the end of each dosing level for titration and treatment (Cohort 1 only)
- Change in coefficient of variation (CV) (ratio of standard deviation: mean) of CGM glucose values over 24 hours from baseline (Day -1) to the end of each dosing level for titration and treatment (Cohort 1 only)
- CV of CGM glucose values over 7 days at each dose level (Days 1 to 7, Days 8 to 14, Days 15 to 21, and Days 22 to 28) (Cohort 1 only)
- Change in percentage of time in hyperglycemia (defined as > 7.8 mmol/l or > 140 mg/dl as measured by CGM) over 24 hours from baseline (Day -1) to the end of each dosing level for titration and treatment periods (Cohort 1 only)
- Change in percentage of time in hypoglycemia (defined as < 3 mmol/l or < 54 mg/dl as measured by CGM) over 24 hours from baseline (Day -1) to the end of each dosing level for titration and treatment periods (Cohort 1 only)

- Percentage of time in hyperglycemia (defined as > 7.8 mmol/l or > 140 mg/dl as measured by CGM) over 7 days at each dose level (Days 1 to 7, Days 8 to 14, Days 15 to 21, and Days 22 to 28) (Cohort 1 only)
- Percentage of time in hypoglycemia (defined as < 3 mmol/l or < 54 mg/dl as measured by CGM) over 7 days at each dose level (Days 1 to 7, Days 8 to 14, Days 15 to 21, and Days 22 to 28) (Cohort 1 only)
- CGM glucose AUC_{0-4hr} during MMTT (type A) on baseline (Day -1) and Day 49 and during MMTT (type B) on Day 7 (Cohort 1 only)
- CGM glucose AUC_{0-2hr} during morning MMTT (type A) on baseline (Day -1) and Day 49 (Cohort 1 only)
- CGM glucose AUC_{0-2hr} during evening MMTT (type C) on baseline (Day -1) and Day 49 (Cohort 1 only)
- The change in insulin AUC_{0-4hr}, glucagon AUC_{0-4hr}, and active and total (the sum of active and inactive GLP-1) GLP-1 AUC_{0-4hr} from baseline (Day -1) to Day 49 (Cohort 1 and 2)
- The change in pre-meal (i.e., time 0 basal/fasting) values of insulin, glucagon, and active and total (the sum of active and inactive GLP-1) GLP-1 from baseline (Day -1) to Day 49 (Cohort 1 and 2)
For Cohort 1 only, the fasting plasma insulin value on Day 7 will also be summarized
- The change in fasting C-peptide from baseline (Day -1) to Day 7 and Day 49 (Cohort 1 only)
- The change in serum beta-hydroxybutyrate concentration from baseline (Day -1) to Days 22 and 49 (pre-dose and 4 hr post-dose) (Cohort 1 only)
- The change in capillary blood ketone concentration from baseline (Day -1) to Days 22 and 49 (pre-dose and 4 hr post-dose) (Cohort 1 only)
- The change in free fatty acids from baseline (Day -1) to Day 49 (Cohort 1 only)
- The change in fasting amino acids from baseline (Day -1) to Day 49 (Cohort 1 only)
- The change in uric acid from baseline (Day -1) to Day 49 (Cohort 1 only)
- [REDACTED]

